Appendix 2 Clinical Laboratory Evaluations

Hematology (performed on whole blood)

Hemoglobin	Mean cell volume
Hematocrit	While blood cell (WBC) & differential
Red blood cell (RBC) count	Platelet count

Chemistry (performed on serum)

Albumin	Glucose
Alanine aminotransferase (ALT)	Lactate dehydrogenase (LDH)
Aspartate aminotransferase (AST)	Total bilirubin
Blood urea nitrogen (BUN)	Total protein
Gamma glutamyl transferase (GGT)	Creatinine
Sodium	Chloride
Potassium	Bicarbonate
Calcium	Phosphorus

Urinalysis (performed on urine)

Ketones	Protein
Specific gravity	Glucose
Potential for hydrogen (pH)	Blood
Appearance	Leukocyte esterase
Bilirubin	Microscopic examination

Other Labs (performed on urine)

Urine culture¹

Urine pregnancy test²

¹ At screening only.

² Urine pregnancy test will only be performed for females of childbearing potential.

Appendix 3 Sample 2-Day Urinary Diary

Instruction to Study Coordinator:

- 1. Complete the **PATIENT Initials** and **PATIENT Number** at the top of each diary page AND on the cover page, prior to providing the diary to the study participant and/or caregiver.
- 2. Instruct the study participant and/or caregiver on how and when to complete the diaryand to return the completed diary at their next visit.

Instructions for Study Participant and/or Caregiver:

- 1. Complete the urinary diary for 2 days in a row (Day 1 and Day 2) prior to your nextvisit.
- 2. Begin each day of the diary with the first catheterization after waking for the dayand continue collecting required information until you/your child wake up the next morning.
- 3. Record the actual date for each day of the diary (day month year). For example:
 - If Day 1 is 03 Jan 2011, then Day 2 will begin with the first catheterization afterwaking on 04 Jan 2011.
- 4. Collect and record the actual volume of *first (morning awakening)* catheterization on Day 1 and Day 2.
 - Use the supplied collection container to collect and measure the urine from *the first (morning awakening)* catheterization.
 - Record the volume of urine collected with *first (morning awakening)* catheterization in cubic centimeters (cc) or milliliters (mL) in the **VOLUME** column of your diary.
- 5. Record the number of catheterizations during the day; note: the volume needs to be recorded only for the first (morning awakening) catheterization.
- 6. Check the **Yes** or **No** box in the **LEAKAGE** column of your diary, indicating if anyleakage occurred since the last catheterization.
- 7. Bring the completed diary with you to your next visit.

Instruction to Study Coordinator upon return of diary:

- 1. Review the diary entries with the study participant and/or caregiver at the start of the visit.
- 2. If additional information is added to the diary to clarify an entry based on your review, include this information and initial/date your entries.

↓ Turn to next page to begin completing diary ↓

EVENT NUMBER	VOLUME Volume of urine collected with first (morning wakening) catheterization	LEAKAGE Did any leakage occur since the last catheterization?	
Cath #10			
Cath #11			
Cath #12			

Appendix 4 Urodynamic Evaluation

The following procedures outline a standard clinical urodynamic evaluation. The Life-Tech Urovision system (or comparable system) with strip chart recording will be used for data collection. All equipment will be appropriately set up and regularly calibrated.

- 1. Patient will report to the urodynamic laboratory at the scheduled time.
- 2. Informed written consent and assent (if applicable) will be obtained from patient and parent/legal guardian.
- 3. After CIC the patient will assume the lithotomy position and will be prepped and draped in a sterile fashion.
- 4. All components of the urodynamic equipment will be checked for proper calibration and function.
- 5. The urethra will be lubricated, and anesthetized with lidocaine jelly, as needed.
- 6. The patient will be catheterized with a triple-lumen urodynamic catheter of a size appropriate for the pediatric patient (the smaller the better).
- 7. A small balloon catheter should be inserted into the rectum to measure intra-abdominal pressure.
- 8. The filling phase of the cystometrogram will be initiated by infusing water or saline through the side-hole channel at a rate of 10-25 mL/min in the supine or sitting position.
- 9. Pressure data from the bladder and rectal catheters will be recorded.
- 10. Captured urodynamic data will include:
 - Maximal bladder capacity
 - Detrusor pressure at maximum bladder capacity
 - Maximum amplitude of involuntary detrusor contractions
 - Volume at first involuntary detrusor contraction
 - Presence (versus total absence) of involuntary detrusor contractions at > 15 cm H2O.

Appendix 5 Anticholinergic Questionnaire

Appendix 6 Vision Symptom Questionnaire for Parent/Caregiver

Visit			
Patient Initials:	Patient #	_	
Place an "X" in the a	ppropriate box as it applies to ye	our child	
Description		(circle Yes or No as indicated)	
Do you suspect anything is wrong with	your child's eye/vision	Yes	No
Has your child ever been diagnosed wi	th an eye condition	Yes	No
Have you observed any problems or ch lashes or the area around the eyes	ange in the whites, pupils, lids,	Yes	No
Has your child shown any signs ofabno dizziness	rmal sensitivity to light or	Yes	No
Has your child had any complaints of n	ausea or headaches	Yes	No
Turning of one eye (in, out, up or down	1}	Ves	No
Poking at the eyes or frequent rubbing		Yes	No
Excessive blinking		Yes	No
Unusual watering or discharge of the e	ye	Yes	No
Poor eye contact		Yes	No
Covering or closing an eye when lookin	ig at an item of interest	Yes	No
Abnormal head posture such as tilting forward or backward when viewing an	the head to one side or moving item of interest	Yes	No
Squinting		Yes	No
Playing the head close to an item of int	aract	Yes	No

Source: Minnesota Department of Health (MDH); Community and Family Health Division; Child and Adolescent Health Unit; Vision Screening Procedures for Infancy, Childhood and School Age Children; June 2014. http://www.health.state.mn.us/divs/cfh/topic/visionscreening/ content/document/pdf/vision_screening_manual.pdf.

Inaccuracy in reaching for an item of interest

If a patient < 8 years old has started treatment and develops visual or ophthalmologic symptoms (ie, blurry vision, dry eye, dilated pupils, constant squinting, eyes drifting outward) it will be recommended that the patient is referred to a pediatric ophthalmologist for a comprehensive eye examination.

Yes

No

Appendix 7 Gel Application Instructions

The instructions below are for gel application by patient or caregiver:

- Bathing or showering should not occur sooner than 1 hour after gel application.
- If bathing before application, the area must be dried completely before gel application.
- Tear open the pouch at the indentation and express the complete contents either into your hand or directly on the abdomen, upper arm/shoulder, or thigh application area (see diagram on following page).
- Gently spread the gel on the application area in a continuous line covering as much of the application area as possible. It should be spread as uniformly and thinly as possible over the entire application area taking care not to transfer any material to any clothing. Care should also be taken not to apply gel to the area in or immediately around the naval during the abdominal applications.
- Gently work the gel into the skin over the entire application area until it dries. Do not continue rubbing after the gel had dried. Within 5 minutes after application, wash your hands thoroughly with soap and warm water.
- After application, the application site should be covered with clothing after the gel has dried (eg, a shirt or pants). In the event that unwashed or unclothed skin to which the gel has been applied comes in direct contact with the skin of another person within a day of application, the general area of contact on the other person should be washed with soap and water as soon as possible.

Gel Application Sites:

Appendix 8 Vision Assessment Instructions for Site

Visual acuity-LEA symbols

- Visual acuity is screened at a distance of 10 feet using the Lea symbols.
- The child need not know these symbols, but must be able to match the indicated symbols on a wall chart with those on the response card.

Equipment

- 10' Lea Vision Chart Student Response Card Flashcards
- Table and chair
- Occluder with lip

Facilities

• Room approximately 15 feet long or greater, well-lit and without glare.

Procedure

Testing the right eye:

- 1. The child must be standing or sitting at a table with the response card in front, eyes at a 10-foot distance from the chart.
- 2. The child must be conditioned to match symbols by pointing to the same symbol on the response card as is being shown with a flash card or pointed to on the chart.
- 3. Begin screening with one person holding an occluder over the child's left eye.
- 4. Another person points to the symbols on the Lea wall chart using caution not to cover the rectangle line with their finger or pointer.
- 5. The child should point to the corresponding symbol on the response card.
- 6. Start with the top line and continue downward showing one letter per line. If the child reaches the bottom line, show the remaining three symbols.
- 7. If the child misses, go to the line above and show four different symbols in that line. If the child matches them correctly, proceed downward.
- 8. To receive credit for a line, the child must correctly match each of the four different symbols on the line.
- 9. The number recorded as the visual acuity is the smallest line the child can read correctly.

Testing the left eye

• Cover the right eye and repeat the procedure

Age five PASS

10/15 or better in each eye without a 2-line difference.

Re-screen/REFER

10/20 or worse in either eye or a 2-line difference in the pass range

Age three to four PASS 10/20 or better in each eye without a 2-line difference

Re-screen/REFER 10/25 or worse in either eye or a 2-line difference in the pass range.

Considerations for screening special populations:

- The matching of the Lea symbols may be practiced before the screening
- For some children with special needs it may be useful to reproduce the response card, cut and space them so that larger movements can be used when indicating the matching symbol.

NOTE: At recheck, the poorer eye should be screened first. Children unable to perform the Lea chart should be given the procedures designed for younger children. Occluders should be cleaned between children.

PRESCREENING PRACTICE SHEET

In order for us to check your child's vision he/she must be able to play a matching game.

- 1. Cut the paper along the dotted lines.
- 2. Place the four large letters (Chart 1) in front of your child.
- Point to a letter on Chart 2 and have your child touch the letter that looks the same on Chart 1. Start with the larger letters and move downward to the smaller.
- 4. Play the game until your child responds correctly and consistently.

Reminders:

- The detection of vision disorders and symptoms during the study will be tracked by the adverse event reporting process. The severity of the event and the relationship to the study drug will be assessed by the investigator and reported on the Adverse Event Form.
- Any patients with asymmetric/unequal or severe refractive error will be excluded from the study since aforementioned conditions can result in refractive amblyopia and may confound the study outcomes.

SEM	standard error of mean
SI	Le Système International d'Unités (International System of Units)
SOC	system organ class
TEAE	treatment-emergent adverse event
WHO	World Health Organization

4. Introduction

This statistical analysis plan (SAP) details comprehensive, technical specifications of the statistical analyses of the efficacy and safety data outlined and/or specified in the final protocol of Study OG09002. Specifications of tables, figures, and data listings are contained in a separate document. Statistical analysis plan for pharmacokinetics data will be addressed separately.

This document is organized into 3 main sections:

[figure not shown]
- 1. Study overview including study design and objectives
- 2. Statistical Methodology and Study Endpoints
- 3. Data Handling and Analysis Conventions

4.1 Study Design Summary

This study was initiated as a double-blind, placebo-controlled study with an open-label extension and was amended via protocol amendment (Protocol Amendment 3) to enroll participants under only open-label treatment. Therefore, analyses are described with respect to prior to protocol amendment 3 ("pre-amendment 3") and with protocol amendment 3 ("post-amendment 3").

Prior to Amendment 3, participants aged 6 years to < 17 years who had a diagnosis of detrusor overactivity associated with a neurological condition and were using clean intermittent catheterization (CIC) to control bladder function were randomly assigned 1:1 to receive doubleblind oxybutynin chloride gel or placebo gel for 6 weeks. Enrollment was stratified based on sex, age, and weight. Stratification was done within the following groups: male and female; 6 to < 12 years-of-age and 12 to < 17 years-of-age; and by weight category: ≤ 25.0 kg and > 25.0 kg for the 6 to < 12 years-of-age group and \le 50.0 kg and > 50.0 kg for the 12 to < 17 years-of age group. Enrollment into the 6-week treatment period was to be followed by an open-label, 8-week period to generate safety data. All participants began treatment with 0.75 g of gel/day for 2 weeks. Participants then returned to the clinic at Week 2 for a potential dose titration and at this time their dose could have been adjusted up to 1 g/day, down to 0.5 g/day, or remained the same at 0.75 g/day. The determination of dose was based on the investigator's clinical judgment and assessment of the patient's bladder symptoms and treatment side effects. Dose titration was permitted only once during the entire 6-week double-blind, placebo-controlled period. Participants continued blinded treatment for 4 additional weeks until the end of the double-blind treatment period.

Post-Amendment 3, the study became a multicenter, open-label, dose-titration study in pediatric participants, ages 3 years to < 17 years, with detrusor overactivity associated with a neurological condition. A minimum of 25 participants are to be enrolled. Efforts will be made to enroll a greater number of participants from the ages of 3 years to < 6 years. Participants must be suitable

[figure not shown]
candidates for anticholinergic therapy and must be using CIC for bladder control. The study will include a screening period from Day -13 to Day -5 and a 14-week open-label treatment period. The expected duration of the study for each patient will be up to 16 weeks (which includes 2 weeks of screening and 14 weeks of treatment). There are six clinic visits (Visit A – Visit F). No changes were made in the starting dose, compared to the Pre-Amendment 3 study design, in that all participants will begin treatment with 0.75 g of gel/day for 2 weeks. Participants will then return to the clinic for a potential dose titration and at this time their dose may be adjusted up to 1 g/day, down to 0.5 g/day, or remain the same at 0.75 g/day, depending on individual response and tolerability. The determination of dose will be based on the investigator's clinical judgment and assessment of the patient's bladder symptoms and treatment side effects. Dose titration will be permitted only once during the entire 14-week treatment period (at Visit C, Week 2). Participants will continue the adjusted dose for 12 additional weeks until the end of the openlabel treatment period.

[figure not shown]
Safety will be evaluated by monitoring adverse events, physical examinations, vital signs, clinical laboratory evaluations, skin erythema at the application site, and a vision symptom questionnaire.

4.2 Study Objectives and Endpoints

Each study objective is presented with endpoint(s) below:

Objectives		Endpoints		
Primary		Primary Efficacy Endpoints		
•	Pre-Amendment 3: To evaluate the efficacy of daily treatment with oxybutynin chloride gel compared to placebo in pediatric participants during the first 6 weeks (i.e., the double-blind treatment period) of a 14-week treatment	•	Change from baseline to Week 6 of treatment or to the last observation carried forward (LOCF) in the percentage of catheterizations without a leaking accident as recorded in the 2-day urinary diary	
	period	S	econdary Efficacy Endpoints	
• Post-Amendment 3: To evaluate the efficacy of daily treatment with oxybutynin chloride gel in pediatric participants during the first 6-weeks of a 14-week open-label treatment period		•	Change from baseline to Week 6 of treatment in the following (calculated from the 2-day urinary diary data): O Average volume of urine collected per catheterization (for Pre-Amendment 3 population only)	
			 Average volume of urine collected at first (morning awakening) catheterization 	
			 Average number of catheterizations per day 	

Allergan

Objectives	Endpoints		
Secondary	Pharmacokinetic Endpoints:		
To evaluate the pharmacokinetics, pharmacodynamics, safety, and skin, tolerability of oxybutynin chloride gel in pediatric participants	 Plasma concentration for Oxybutynin (OXY) and N-desethyloxybutynin (DEO) plasma concentrations for the R- isomer, S-isomer, and R+S The ratio of DEO to OXY Safety Assessments: Adverse events (AE), clinical laboratory values, vital signs, and physical examinations Skin Tolerability of Oxybutynin Assessment: Skin assessments for Erythema Other Assessments: Anticholinergic Symptoms Questionnaire Vision Symptom Questionnaire 		

4.3 Schedule of Events

Post-Amendment 3

	Screening Period		Open-Label Treatment Period				
	Visit A ¹	Visit B	Visit C	Visit D	Visit E	Visit F/ ET	
Evaluation:	-13 to -5 Days	Week 0	Week 2	Week 6	Week 10	Week 14	
Informed Consent	X						
I/E Criteria	X	X					
Medical History	X	X					
Vision Assessment in Children < 8 years	X^2						
Concomitant Medication	X	X	X	X	X	X	
Demographic Information	X						
Physical Examination	X					X	
Height and Weight	X						
Vital Signs	X	X	X	X	X	X	
12-Lead ECG	X						
Serum Chemistries	X					X	
Hematology	X					X	
Urinalysis	X	X^3				X	
Urine Culture	X						
Urine pregnancy test ⁴	X			X		X	
Urodynamics		X		X			
Dispense 2-day Urinary Diary	X		X				
Collect 2-day Urinary Diary		X		X			
Local Erythema Assessment ⁵			X	X	X	X	
Adverse Event Assessment			X	X	X	X	
Anticholinergic Questionnaire		X	X	X	X	X	
Vision Symptom Questionnaire		X	X	X	X	X	
Collect PK Sample & Record Date/Time			X	X		X	
Dose Titration (if necessary)			X				
Study Drug Dispensing		X^6	X^6	X	X		
Study Treatment Compliance			X	X	X	X	

SAP OG09002 Oxybutynin Chloride 10% Gel

- All participants taking anticholinergic medications will be asked to discontinue treatment and complete a 3-day washout period (11-day washout period if the patient was previously taking solifenacin).
- 2 Vision Assessment is required prior to or at the Baseline Visit for participants < 8 years of age, at the time of screening who have not received a vision screening assessment within the last 12 months prior to screening.
- 3 A urine sample for on-site urinalysis to determine presence of bacterial infection will be collected.
- 4 Urine pregnancy test will only be performed for females of childbearing potential.
- 5 Assessment for local erythema at application site.
- 6 Instruct patient/caregiver on study treatment application.

Pre-Amendment 3

The schedule of events for Pre-Amendment 3 is found in Appendix 1 of this document.

5. Statistical Methodology and Study Endpoints

5.1 Statistical Methods Planned in the Protocol and Determination of Sample Size

This SAP will be approved prior to database lock. The SAP expands the statistical section of the protocol and contains a detailed description of methods to analyze data collected in the study. The text portion of the SAP will be included in the CSR report as Appendix 16.1.9.

5.1.1 Statistical and Analytical Plans

Statistical analyses will be conducted using SAS Version 9.3 or newer.

5.1.1.1 Common Conventions

5.1.1.1.1 Analysis Populations

The analysis populations will consist of participants as defined below, where analysis populations are formed relative to the protocol under which a participant was enrolled. Participants enrolled prior to protocol amendment 3 are referred to as "pre-amendment 3," and participants enrolled under protocol amendment 3 or later are referred to as "post-amendment 3." For example, the pre-amendment 3 safety population consists of all treated participants who received blinded study treatment and may have also received open-label active treatment. The post-amendment 3 safety population consists of all treated participants who received open-label active treatment. Details are below with categorizations based on double-blind or open-label treatment.

[figure not shown]

Table 5-1 Analysis Populations

Population	Definition	Study Treatment
Post-Amendment 3 open- label Safety	All participants who receive at least 1 dose of study treatment in the open-label period who are enrolled under Amendment 3 or	Actual received ¹
Pre-Amendment 3 double-blind Safety	All participants who receive at least 1 dose of study treatment in the double-blind period, which is only applicable to participants who enrolled prior to Amendment 3	Actual received ¹
Pre-Amendment 3 open- label Safety	All participants who receive at least 1 dose of study treatment in the open-label period before Amendment 3	Actual received ¹
Combined open-label Safety (Pre- and Post- Amendment 3)	All participants who receive at least 1 dose of study treatment in the open-label period before or after Amendment 3	Actual received ¹
Post-Amendment 3 Intent-to-Treat (ITT) ²	All participants who receive at least 1 dose of study treatment and have at least one post-baseline value for the primary efficacy variable in the Post-Amendment 3 open-label period	Actual received ¹
Pre-Amendment 3 (Intent-to-Treat) ITT ²	All randomized participants who have at least one post-baseline value for the primary efficacy variable in the Pre-Amendment 3 double-blind period	Randomized assignment
Combined Intent-to-Treat (ITT²) (Pre- and Post-Amendment 3)	All participants who receive at least 1 dose of study treatment and have at least one post-baseline value for the primary efficacy variable in the Post-Amendment 3 open-label period and all randomized participants who have at least one post-baseline value for the primary efficacy variable in the Pre-Amendment 3 double-blind period	Actual received or Randomized assignment ³
Post-Amendment 3 Per- Protocol (PP)	All participants in the Post-Amendment 3 ITT population who complete the Post-Amendment 3 open-label treatment period of the study and who are without significant protocol violations	Actual received ¹
Pre-Amendment 3 Per- Protocol (PP)	All participants in the Pre-Amendment 3 ITT population who complete the double-blind treatment period of the study and who are without significant protocol violations	Randomized assignment

- 1 Participants will be summarized according to the study treatment received for majority of the treatment period.
- The primary efficacy variable in the description of each ITT population definition is the change from baseline (CFB) to Week 6 of treatment or the last observation carried forward (LOCF) in the percentage of catheterizations without a leaking accident as recorded in the 2-day urinary diary.
- 3 Actual treatment received for Post-Amendment 3 open-label data and Randomized treatment for Pre-Amendment 3 double-blind treatment period data.

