11.2 Analysis Populations and Databases

Statistical analysis and data tabulation will be performed using *data from the open-label period for patients enrolled after Amendment 3 and the data from the double-blind and open-label periods for patients enrolled prior to Amendment 3 in* the following patient populations unless specified otherwise:

- Safety populations:
 - Post-Amendment 3 open-label safety population
 - Pre-Amendment 3 double-blind safety population
 - Pre-Amendment 3 open-label safety population
 - Combined open-label safety population (Pre- and Post-Amendment 3)
- Intent-to-treat (ITT) populations:
 - Combined ITT population (Pre- and Post-Amendment 3; primary efficacy analysis population)
 - Post-Amendment 3 ITT population
 - Pre-Amendment 3 ITT population

- Per-protocol (PP) populations:
 - Post-Amendment 3 PP population
 - Pre-Amendment 3 PP population
- PK populations:
 - Post-Amendment 3 PK population
 - Pre-Amendment 3 PK population
 - Combined PK population (Pre- and Post-Amendment 3)

The *Post-Amendment 3 open-label* safety population is defined as all *patients* who receive at least *1* dose of *study treatment in* the open-label period *after Amendment 3*.

The Pre-Amendment 3 double-blind safety population is defined as all patients who receive at least 1 dose of study treatment in the double-blind period before Amendment 3.

The Pre-Amendment 3 open-label safety population is defined as all patients who receive at least 1 dose of study treatment in the open-label period before Amendment 3.

The combined open-label safety population is defined as all patients who receive at least 1 dose of study treatment in the open-label period before or after Amendment 3.

The primary efficacy analysis populations will be the *Post-Amendment 3* ITT population *and the Pre-Amendment 3 ITT population*.

The combined ITT population will include all patients who have a baseline value for the primary efficacy variable in the Post-Amendment 3 open-label period or all randomized patients who have a baseline value for the primary efficacy variable in the Pre-Amendment 3 double-blind period.

The Post-Amendment 3 ITT population will include all randomized patients who have a baseline value for the primary efficacy variable in the Post-Amendment 3 open-label period.

The *Pre-Amendment 3* ITT population will include all randomized patients who have a baseline value for the primary efficacy variable *in the Pre-Amendment 3 double-blind period*.

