The *Pre-Amendment 3* PP population will include all *patients* in the *Pre-Amendment 3* ITT population who complete the *double-blind* treatment period of the study and who are without significant protocol violations.

The Post-Amendment 3 PP population will include all patients in the Post-Amendment 3 ITT population who complete the Post-Amendment 3 open-label treatment period of the study and who are without significant protocol violations.

The PK population will include all *patients* who have at least 1 sample draw for plasma concentrations. The PK population will only be used in the summary statistics and analyses of the *PK* data.

Additionally, 2 types of visits are defined for the purposes of analysis and summary:

- Observed cases (OC)
- Last observation carried forward (LOCF)

The OC visits are defined to be those assessment values observed at each scheduled visit. All applicable efficacy and safety variables will be summarized using the OC visits.

The LOCF visit is defined as the last data recorded for each efficacy variable. This visit will be *designated as* Week 6 (LOCF). *The Week 6 (LOCF) visit will be defined for the Post-Amendment 3 open-label period and the Pre-Amendment 3 double-blind period* and will only be used to summarize efficacy data. The LOCF visit provides missing value imputation for *patients* who do not complete the *open-label treatment period (Post-Amendment 3) or the double-blind treatment period (Pre-Amendment 3)* of the study and will include all *patients* in the *corresponding* ITT population.

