5.1.1.1.4 Missing Data

General missing data handling conventions for methodologies in Section 5.1.1.1.3 are summarized as follows:

Table 5-3 Missing Data Handling by Endpoint Type

Parameter type	Timing	Missing Data Handling
CFB ANCOVA	Treatment Period	 If missing a covariate: ○ Participant excluded If missing derived value at the specified post-baseline analysis visit: ○ Available cases (i.e., observed case [OC] analysis) ■ Participant excluded ○ Last observation carried forward (LOCF) ■ Participant included using LOCF-imputed value (last non-missing post-baseline value before the missing value is carried forward to impute the missing value). Baseline value will not be carried forward.

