5.2 Changes in the Conduct of the Study or Planned Analyses

At the time of writing this SAP, there were no changes in study conduct from what is described in the protocol and protocol amendments. Changes to planned analyses from what was described in the protocol are detailed in this SAP as described in Section 5.2.2 below.

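### The protocol and SAP define the primary ITT sets differently and are not reconciled, and the SAP gives a Post-Amendment 3 early-termination diary before Day 29 no analysis visit

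*SAP*

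**What the plan says.** **Protocol 11.2 (Amendment 4, 31 October 2022).** Entry to each ITT set rests on a baseline value. For the combined set: "The combined ITT population will include all patients who have a baseline value for the primary efficacy variable in the Post-Amendment 3 open-label period", plus randomised Pre-Amendment 3 children with a baseline value. For the open-label part alone: "The Post-Amendment 3 ITT population will include all randomized patients who have a baseline value for the primary efficacy variable". On LOCF: "The LOCF visit is defined as the last data recorded for each efficacy variable". The same paragraph says the LOCF visit takes in every patient of the corresponding ITT set.

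**SAP Table 5-1 (latest version listed in 5.2.2: 2.0, 28 March 2022).** All three ITT rows require a post-baseline value. Post-Amendment 3 children must have had a dose and must "have at least one post-baseline value for the primary efficacy variable in the Post-Amendment 3 open-label period". Footnote 2 adds: "The primary efficacy variable in the description of each ITT population definition is the change from baseline (CFB) to Week 6 of treatment", or its LOCF value.

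**SAP Table 5-3.** LOCF uses the "last non-missing post-baseline value before the missing value is carried forward to impute the missing value", and "Baseline value will not be carried forward".

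**Record of changes.** SAP 5.2 states: "Changes to planned analyses from what was described in the protocol are detailed in this SAP as described in Section 5.2.2 below". The 5.2.2 list has no entry on the ITT definitions; its only entry on analysis populations concerns the demographics tables.

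**Diaries.** Before Amendment 3, post-baseline diaries were collected at Weeks 2 and 6 (SAP Appendix 1), with a Day 2-28 window for Week 2 (Table 6-2). After Amendment 3, protocol 9.6.1 schedules one post-baseline diary, before Visit D at Week 6, and the only post-baseline window in Table 6-3 opens at Day 29. Protocol 9.5.4 has a diary already handed out collected at an early-termination visit that directly follows.

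**The concern.** Two matters need separating.

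The first is textual. The protocol and SAP give different denominators for sets with the same name, and one of those sets carries the primary analysis. The later-dated document does not adopt the SAP's rule, and the section where the SAP says departures are recorded does not mention it. If this stays open until after data are seen, the choice of set becomes discretionary.

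The second concerns who supplies a Week 6 (LOCF) value. SAP 5.1.1.3.1 pools both gel groups against Pre-Amendment 3 placebo when the Kolmogorov-Smirnov check gives p of 0.05 or more. A Pre-Amendment 3 child on either arm who stops between the two diaries still has a Week 2 value to carry. A Post-Amendment 3 child who stops in the same interval has no scheduled diary behind them. If such children do worse than completers and are left out, the pooled gel mean rises with no corresponding change on placebo.

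**Working it through.** **Plan's own figure.** Inputs from SAP 5.1.2: SD 28, means 25 and 5, 48 per arm, 10% dropout. Alpha 0.05 two-sided is assumed, because the sample-size text does not state it. The noncentral t gives 93.4% power at 48 per arm (plan: 93%) and 90.6% at 43 per arm (plan: 90%), so the inputs are read correctly.

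**Who has a value under the SAP, by time of stopping.**

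| Stops | Pre-Amendment 3, both arms | Post-Amendment 3 gel |
|---|---|---|
| Before the Week 2 diary | no value | no value |
| Between the Week 2 and Week 6 diaries, no diary at termination | Week 2 value carried | no value |
| Same interval, termination diary on Day 15-28 | Week 2 value or later | unclear: Table 5-3 names no window, Table 6-3 has no visit |
| Same interval, termination diary on Day 29 or later | Week 6 window | Week 6 window |

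The one-sided loss is confined to the second row and, on one reading, the third.

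**Which rule causes it.** Suppose Table 5-1 were changed to the protocol's baseline rule and Table 5-3 left alone. The ANCOVA would still lack a value for these children and would exclude them. The set wording by itself changes only the stated denominator.

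**Size in the pooled analysis.** The documents do not give the missingness, so this is an unadjusted illustration. Assumptions: gel completers change by 25; gel stoppers change by 0 in both parts; the same stop rate d in both parts; all stopping falls between the two diaries; no termination diary is used; 25 Post-Amendment 3 children (the plan's minimum); N Pre-Amendment 3 gel children, taken as 48 (planned), 24 or 12, because the actual number is not stated.

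- Everyone counted: gel mean = 25(1-d).
- SAP set: gel mean = 25(1-d)(N+25) / (N+25(1-d)).
- Inflation = 25(1-d) × 25d / (N+25(1-d)).

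At d = 0.10 and N = 48: 22.5 × 2.5 / 70.5 = 0.80.

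| d | N = 48 | N = 24 | N = 12 |
|---|---|---|---|
| 5% | 0.41 | 0.62 | 0.83 |
| 10% (plan's dropout rate) | 0.80 | 1.21 | 1.63 |
| 20% | 1.47 | 2.27 | 3.12 |

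With placebo completers at 5 and placebo stoppers kept at 0, the placebo mean at 10% is 5 × 0.9 = 4.5. The gel-placebo difference is then 22.5 - 4.5 = 18.0 with everyone counted, and 18.8, 19.2 or 19.6 in the SAP set.

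**Against sampling error.** With SD 28, the standard error of the pooled difference is 28 × √(1/(N+25) + 1/N), with N on placebo: 5.2, 7.0 and 9.3. The 10% row is therefore about 0.15 to 0.18 of a standard error.

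**Milder assumptions.** If stoppers change by s, the inflation scales by (25-s)/25, so s = 12.5 halves every entry. If in addition half the stoppers return a usable diary, the 10% row falls to 0.20, 0.29 and 0.39. If no Week 6 diary is missing it is zero.

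**If the parts are analysed separately.** The same selection touches only the Post-Amendment 3 one-sample t-test. At 10%, the mean is 25 with stoppers excluded against 25 × 0.9 = 22.5 with them counted at zero.

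**The case against.** The strongest reply is that the definitional conflict, taken alone, moves no estimate. The protocol says LOCF covers all ITT patients but never says what score a child without an on-treatment diary receives. If it gives none, its own ANCOVA drops the same children and the documents differ only in the denominator. This stands, and it is why the ITT wording should not be named as the cause of the loss.

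Second, protocol 9.5.4 already offers a partial rescue. Children stopping after Visit C hold a diary handed out there, and since neither Table 5-1 nor Table 5-3 names a window, the plainer reading may be that a Day 15-28 diary counts. This stands in part: it shrinks the group at risk, but Table 6-3 gives such a diary no visit, so the point remains undecided.

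Third, the illustration is severe. Pre-Amendment 3 gel stoppers would carry a Week 2 value recorded on active gel, unlikely to be exactly zero, and 20% is twice the only dropout rate in the plan. This also stands.

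Fourth, SAP Tables 5-4 and 5-5 already report set membership by part and treatment, with discontinuation reasons. That helps a reader see losses but does not settle which set is primary.

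A reader might infer more than the documents support. They do not show that the SAP rule removes early stoppers from gel alone: those who stop before the Week 2 diary are lost in both parts and both arms. Nor do they show a concealed change: 5.2.2 is a log by SAP version, and when the post-baseline rule entered cannot be seen.

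**Conclusion.** The conflict is real and bears on the primary analysis set: baseline value in the protocol, post-baseline value in the SAP, no entry in 5.2.2, and a later protocol amendment that keeps its own rule. Confidence in this is high.

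The gap for early-termination diaries is also real but narrow. In a pooled analysis it can leave out some Post-Amendment 3 gel children who stop between the Week 2 and Week 6 time points, with no matching loss on placebo. The source is the missing-data rule together with a single scheduled diary.

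The resulting bias is likely small. The 0.8 to 1.6 points at 10% stopping rest on assumed outcomes, timing and numbers that the documents do not supply, and milder assumptions reduce them. It would be wrong to conclude that the trial's efficacy result is materially inflated. The randomised Pre-Amendment 3 comparison is untouched by this selection and, under SAP 5.1.1.3.1, is reported either as the primary or as a supplementary analysis.

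This should be corrected before database lock, as a matter of a clear and pre-stated analysis set more than of expected bias.

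**What to change.** Before database lock:

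1. Reconcile the ITT definition and the LOCF rule together, in both documents; changing the ITT wording alone would restore no one. If the SAP set stays primary, call it modified ITT, enter the change and its reason in 5.2.2, and report exclusions by arm, part and reason. While that text is open, the reference to randomised patients in the protocol's Post-Amendment 3 ITT definition can be corrected, since that part has no randomisation.
2. Add a Day 2-28 row to Table 6-3 that feeds Week 6 (LOCF), so that an early-termination diary counts. It will catch only such diaries, because none is scheduled in that interval.

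Optional: a sensitivity analysis on the baseline-only set, under a stated assumption for children with no on-treatment diary. Zero change is one choice, with two known weaknesses. It understates variance: at 10% missing per arm, the arm variances are 0.9 × 28² + 0.09 × 25² = 761.85 and 0.9 × 28² + 0.09 × 5² = 707.85, a pooled SD of 27.1 instead of 28. It is also not always conservative. At 48 per arm, with 10% missing in each arm, power is 89.6% against 90.7% under exclusion; with 10% missing on gel and 20% on placebo, it is 92.5% against 88.9%.

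The cost is protocol and SAP wording and one table row, plus one analysis if the option is taken. No new data are needed.
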